## **D.7. RANDOMIZATION PROCEDURES**

We plan to use stratified cluster-randomization to allocate general surgery residency programs to the two study arms to help ensure balance of programs with respect to prior levels of resident burnout. We anticipate that there is a range of extant wellness activities across general surgery residency programs prior to the start of the SECOND Trial. The concern is that chance allocation may result in an imbalance of residency programs across study arms with respect to previous experience/activity in addressing resident wellness issues.

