### **D.11.2. Program Wellness Initiatives Inventory Survey**

On April 3, 2019, personalized links to the Program Wellness Initiatives Survey were emailed to all ACGME-accredited general surgery program directors. A reminder was sent to non-responders on June 12, 2019. A reminder to enrollees who had not yet completed the survey was sent following enrollment closing and prior to release of the program-specific report. Completion of the survey is a prerequisite for SECOND Trial enrollment.

The Program Wellness Initiatives Inventory Survey queries program directors about existing activities, resources, education, training, policies, and perceptions of problems ([Appendix 4](#)). It will be distributed via Qualtrics annually to assess what programs, both Control and Intervention, are doing to address well-being.

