#### F.3.1.2. Adjusted Analyses

Covariate adjustment in evaluations of randomized trials is generally done for purposes of increasing statistical efficiency by reducing variance within treatment groups. Covariate adjustment is also sometimes also undertaken on the basis of chance imbalance of baseline characteristics between study groups. Although programs will be randomized to treatment arms in this study, we anticipate considerable variation in the number of ABSITE respondents per program. In the 2019 ABSITE data, the average program had 23 resident respondents (mean=23.11, SD=11.15; coefficient of variation=48%), but the range spanned from a minimum of 3 residents per program to a maximum of 59 residents per program. Such dispersion in cluster sizes may lead to imbalance of resident characteristics

Thus, our analytic approach to evaluating our primary hypothesis will be to estimate a 2-level hierarchical linear model of the general form:

$$y_{ij} = \alpha_0 + \beta_0 TREAT_j + \beta_1 x_{1ij} + \beta_2 x_{2ij} + \cdots + \beta_k x_{kij} + \gamma_1 z_{1j} + \cdots + \gamma_m z_{mj} + \zeta_j + \epsilon_{ij}$$

where  $y_{ij}$  is the burnout T-score of resident  $i$  in program  $j$ ,  $TREAT_j$  is the study arm assignment of program  $j$ , and  $x_{1ij}$ - $x_{kij}$  are resident-level covariates and  $z_{1j}$ - $z_{mj}$  are program-level covariates to be adjusted for, including sampling stratification variables. In this model, under randomization of programs to study arms, the coefficient  $\beta_0$  is the adjusted population-averaged intent-to-treat estimate of the effect of assignment to intervention on mean resident burnout. A coefficient  $\beta_0 < 0$  that is statistically

significant with a one-tailed  $p<0.0443$  provides evidence supporting the effectiveness of the intervention over usual care. Other parameters in the model are the constant ( $\alpha_0$ ), coefficients on other resident-level covariates ( $\beta_1-\beta_k$ ), coefficients on program-level covariates ( $\gamma_1-\gamma_m$ ), program-level random intercepts ( $\zeta_j$ ) and individual-level errors ( $\epsilon_{ij}$ ).

Covariates may include variables listed in §E.3.: resident gender; resident relationship status; resident race; program type; program size; and randomization variables such as the quartile of program  $j$  ranked by 2019 program-level mean burnout scores. This list of covariates is subject to change.

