Covariates will not include any other resident-level outcome or behavioral variable(s) that may be affected by the intervention as doing so may introduce endogeneity. Thus, for example, measures of career satisfaction, duty hour adherence, mistreatment, discrimination/harassment etc. will not be considered as controls in the evaluation of burnout.

Any structural measures – i.e., measures of program characteristics, policy, and/or programs related to burnout will not be controlled for in the primary analysis as doing so might over-control and attenuate the intent-to-treat estimate of the treatment assignment effect.

We will examine the mean, median, skewness and kurtosis values of the dependent variable to assess the normality of the dependent variable. If there is evidence of non-normality in the dependent variable, we may consider an appropriate transformation of the dependent variable; however, generalized linear mixed models are flexible and can accommodate alternative distributional assumptions regarding  $y_{ij}$  without altering the original scale of  $y_{ij}$ .

In accordance with the decision of the Principal Investigators, estimates from the adjusted analyses of the primary outcome will be reported as the primary findings of this study, although both adjusted and unadjusted analyses will be conducted.

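### The primary model's ban on structural measures has no time limit, so its over-control reason also excludes baseline wellness activity and sits awkwardly with the listed program covariates

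*SAP*

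**What the plan says.** F.3.1.2 makes the adjusted two-level model the source of the headline result and gives three statements about its covariates.

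- **Covariate list:** "Covariates may include variables listed in §E.3.: resident gender; resident relationship status; resident race; program type; program size; and randomization variables". The model equation has program-level terms, and the list is said to be subject to change.
- **Resident-level exclusion:** "Covariates will not include any other resident-level outcome or behavioral variable(s) that may be affected by the intervention".
- **Program-level exclusion**, covering any structural measure: "measures of program characteristics, policy, and/or programs related to burnout will not be controlled for in the primary analysis", on the ground that "doing so might over-control and attenuate the intent-to-treat estimate of the treatment assignment effect".

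Elsewhere, D.7 gives the reason for stratifying: "chance allocation may result in an imbalance of residency programs across study arms with respect to previous experience/activity in addressing resident wellness issues". D.7.2 stratifies on 2019 mean burnout, which it assumes reflects prior wellness engagement to some degree. D.11.2 describes the Program Wellness Initiatives Inventory, first sent on 3 April 2019, which asks about existing activities, resources and policies. It says: "Completion of the survey is a prerequisite for SECOND Trial enrollment". Section H dates randomization to November 2019.

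**The concern.** Over-control arises when a model conditions on something that lies between assignment and outcome. A value fixed before randomization cannot lie there. The resident-level exclusion uses the right test, namely whether the intervention may affect the variable. The program-level exclusion drops that test and bars a class of measures whenever they were recorded.

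Two things follow. First, the inventory measures wellness programs and policies, so it is barred on any reading, although it measures directly what D.7 worries about. G.1 says both arms probably already run such programs and will keep them, so background activity is a plausible source of chance imbalance. Second, program type and size are program characteristics. On a literal reading they are permitted by one paragraph of F.3.1.2 and excluded shortly afterwards. Two analysts could follow the text and fit different primary models.

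**Working it through.** **1. The plan's own figure.** Exhibit D.8.B gives a detectable difference of 0.86 T-score points for 110 programs per arm and 20 residents per program. Its inputs are SD 9.027, ICC 0.012, alpha 0.0443 and power 80%. The formula is

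MDD = (z for 1 − alpha/2 + z for 0.80) × SD × √(2 × [1 + (m − 1) × ICC] / (k × m)).

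With k = 110 and m = 20, the design effect is 1 + 19 × 0.012 = 1.228 and the MDD is 0.860, which matches. All 12 rows reproduce to within 0.005 with a two-sided alpha. A one-sided alpha gives 0.767 for this row and does not reproduce the table.

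**2. Where the ICC of 0.012 comes from.** D.8.3 and Exhibit D.8.A show that the adjusted planning model contained region, program type and program size as well as strata and resident covariates. The ICC is 1.010 / (1.010 + 81.485) = 0.012. With strata only it is 1.821 / (1.821 + 83.721) = 0.021, with SD 9.150.

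**3. Loose upper bound for losing the program covariates.** With strata only, the design effect is 1 + 19 × 0.021 = 1.399 and the MDD is 0.931. The ratio is 0.931 / 0.860 = 1.08, and power at 0.86 is about 73%. This overstates the loss for two reasons:

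- The strata-only model also drops the resident covariates, and it was fitted to 5,962 residents in 300 programs against 5,075 in 237.
- In Exhibit D.8.A the program covariates at issue have intervals that include zero: community −0.069 (−0.810 to 0.672), military −0.322 (−1.985 to 1.341), size 0.125 (−0.056 to 0.306). Those for female (2.064) and non-white (−1.512) do not.

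**4. Possible gain from the inventory.** The document reports no relation between the inventory and burnout, so this step rests on an assumption. Take the inventory to explain 10-30% of the Level-2 variance remaining after stratification.

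- Variance of a program mean at 20 residents: 1.821 + 83.721 / 20 = 6.007.
- Removed: 0.182 to 0.546, or 3% to 9% of 6.007.
- Effect on the detectable difference: √(1 − 0.0303) = 0.985 and √(1 − 0.0909) = 0.953, a fall of 1.5% to 4.7%.
- Applied to 0.931, this gives about 0.917 to 0.888.

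As an outer limit, a covariate that removed all remaining program variance from the adjusted model (ICC 0.012 to 0) would lower the MDD from 0.860 to 0.776.

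**5. Timing of the inventory.** D.11.2 also records a reminder, after enrollment closed and before the program reports were released, to enrollees who had not completed the survey. Section H puts randomization in November 2019 and report delivery in December 2019. Some forms may therefore post-date randomization, despite the prerequisite.

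**The case against.** The strongest defence is that the sentence is loosely worded but its aim is clear. The phrase about a relation to burnout may govern all three nouns, so the target would be wellness structures on the causal path. The preceding paragraph is limited to variables the intervention may affect, and the covariate list names type, size and the burnout quartile outright. On that reading type and size were never at risk, and the conflict is an ambiguity rather than a flat contradiction. That stands, but the ambiguity still concerns the primary model, and the inventory is excluded either way.

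A reader might infer that the model cannot account for prior wellness activity at all. The document does not support this. The strata are in the model, were chosen for this purpose, and cut Level-2 variance by 75% in the planning data. Only direct adjustment is missing. Baseline activity may also enter the optional interaction analyses (F.3.3.2), and the optional instrumental-variable analysis (F.3.3.4) depends on what was already in place.

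A reader might also infer bias. Under randomization, omitting a baseline covariate does not bias the intent-to-treat estimate, and existing activity in both arms is part of the pragmatic contrast.

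Nor can a baseline inventory be assumed on file for every program, given the late reminder. The document defines no inventory score, so any such covariate would have to be constructed.

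**Conclusion.** The point holds as a defect of wording with a modest statistical cost. The exclusion rests on a reason that cannot apply to values fixed before randomization, and it shuts out the direct baseline measure of the plan's own stated concern. Its literal scope overlaps the covariate list and the planning model.

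The consequence is some lost precision and chance imbalance left unadjusted in the headline estimate. The amount cannot be derived from the document. The 1.5-4.7% reduction in detectable difference rests entirely on the assumed 10-30% and on the strata-only variance components. The 8% shift from 0.86 to 0.93 should not be read as the price of the rule. It is only a loose ceiling on losing the program covariates, because it mixes in resident covariates and a different sample.

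**What to change.** In F.3.1.2:

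1. Limit the exclusion to structural, policy or program measures recorded after randomization, matching the test used for resident-level variables.
2. State that baseline program type, program size and the randomization strata stay in the primary model. Correct the cross-reference as well, since resident and program characteristics are listed in E.4, not E.3.
3. Prespecify one simple baseline inventory measure, such as the number of wellness initiatives in place, as a program-level covariate. Use only forms completed before randomization, and put all other programs in a missing category so that none is lost from the complete-case analysis. Whether a form was completed before randomization is itself fixed before assignment, so the category is safe to adjust for.

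The cost is a reworded sentence, a check of form completion dates, and one or two program-level degrees of freedom among 209 programs. If the inventory turns out to be unrelated to burnout, little is lost.

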#### ***F.3.1.3. Program-Level Analyses***

To assess the robustness of our findings across alternative modeling approaches, we will also evaluate the effect of assignment to Intervention on aggregate, program-level mean burnout T-scores. For these analyses, we will construct mean burnout T-scores for each program in the study. We will then regress mean program burnout T-scores on a dichotomous variable indicating study arm assignment, as well as randomization strata as follows:

$$\text{MeanBurnout}_j = \alpha + \beta_0 \text{TREAT}_j + \gamma_1 Q_{2j} + \gamma_2 Q_{3j} + \gamma_3 Q_{4j} + \nu_j$$

where  $\text{MeanBurnout}_j$  is the mean burnout score in program  $j$ ,  $\text{TREAT}_j$  is the study arm assignment of program  $j$ , and  $Q_{2j} - Q_{4j}$  are randomization strata (assuming quartiles of previous year's mean burnout scores are used for stratification, with  $Q_{1j}$  omitted as the reference category). Here,  $\beta_0$  is the intent-to-treat estimate of the effect of assignment to Intervention on mean program burnout rates, and we hypothesize  $\beta_0 < 0$ .

We may additionally estimate adjusted program-level regressions by incorporating program-level covariates into the model above.

We anticipate estimating this program-level model using ordinary least squares (OLS) regression, pending assessment of program-level mean burnout T-scores for normality. In the 2019 ABSITE data,

program-mean burnout T-scores had a skewness of -0.558 and kurtosis of 3.587. Shapiro-Wilk, Shapiro-Francia, and skewness-kurtosis tests for normality were significant. Decisions regarding modeling and transformation of the dependent variable will depend on the normality of program-level mean burnout scores in the actual study data, as well as considerations of statistical assumptions and interpretability of results.

### **F.3.2. Analysis of Secondary Outcomes**

As discussed in §C.2 and §E.2, a number of secondary endpoints may be evaluated pertaining to resident wellbeing, resident education, and patient outcomes.

##### *F.3.2.1.B. Component Items of Areas of Work-Life*

As discussed in §C.2, responses to individual survey items comprising each of the 9 domains may themselves be analyzed as secondary outcomes. Most of these component items are measured on a Likert-type scale and are thus ordered categorical variables. Several analytic approaches may be taken in the evaluation of these component outcomes.

A two-level hierarchical ordered logistic regression model can be estimated to model the log-odds that a resident will select a response category above a level  $s$  as a function of study arm assignment, resident

characteristics, program characteristics, and program intercepts. The general form of these models would be:

$$\log \left( \frac{Pr(y_{ij} > s | TREAT_j, x, z, \zeta_j)}{(1 - (Pr(y_{ij} > s | TREAT_j, x, z, \zeta_j)))} \right) = \beta_0 TREAT_j + \beta_1 x_{1ij} + \beta_2 x_{2ij} + \dots + \beta_k x_{kij} + \gamma_1 z_{1j} + \dots + \gamma_m z_{mj} + \zeta_j - \kappa_s$$

where  $y_{ij}$  is the response of resident  $i$  in program  $j$ ;  $x_{1ij} \dots x_{kij}$  are resident-level covariates and  $z_{1j} \dots z_{mj}$  are program-level covariates to be adjusted for, including sampling stratification variables,  $\zeta_j$  are program intercepts, and  $\kappa_s$  are category cutoff parameters. Such models can, in theory, be estimated using generalized linear latent and mixed models (*gllamm*) in *Stata*. In practice, such models are computationally intensive and are unlikely to be practical. Moreover, ordered logistic regression rests on the assumption of proportional odds: that is, the association between a covariate and the outcome is constant across categories. There is no ready way to test or address this assumption following estimation of a hierarchical ordered logistic regression in *Stata*.

A more practical approach will be to estimate a non-hierarchical generalized ordered logistic regression as above, with robust clustered standard errors to account for program-level clustering. Generalized ordered logistic regression estimates a single set of parameters for variables that meet the proportional odds assumption. For those variables that violate this assumption, generalized ordered logistic regression estimates separate parameters for each level.

Interpreting and reporting the results of generalized ordered logistic regression models can be cumbersome. For an outcome with 5 response categories, up to 5-1=4 parameters may be estimated for each covariate that violates the proportional odds assumption. For outcomes with 7 response categories (e.g. mistreatment survey items), up to 6 parameters may be estimated for each covariate that violates the proportional odds assumption. Thus, a more practical approach may be to dichotomize these ordered categorical variables. Dichotomization will permit estimation of hierarchical logistic regression equations of the general form:

$$\log \left( \frac{Pr(y_{ij} = 1 | TREAT_j, x, z, \zeta_j)}{(1 - (Pr(y_{ij} = 1 | TREAT_j, x, z, \zeta_j)))} \right) = \beta_0 TREAT_j + \beta_1 x_{1ij} + \beta_2 x_{2ij} + \dots + \beta_k x_{kij} + \gamma_1 z_{1j} + \dots + \gamma_m z_{mj} + \zeta_j$$

where  $y_{ij}$  is the response of resident  $i$  in program  $j$ ;  $x_{1ij} \dots x_{kij}$  are resident-level covariates and  $z_{1j} \dots z_{mj}$  are program-level covariates to be adjusted for, including sampling stratification variables and  $\zeta_j$  are program intercepts.

Alternatively, or perhaps additionally, non-hierarchical logistic regression equations may be estimated with robust standard errors that account for non-independence of observations within programs.

#### *F.3.2.1.C. Education Outcomes*

As discussed in §C.2.2, responses to individual survey we will also evaluate the effect of randomization to intervention on various resident educational outcomes, including ABSITE scores, ABS Qualifying

Examination (QE) scores, ABS Certifying Examination (CE) scores, ACGME case log data, and ACGME annual resident and faculty surveys.

Some of these outcomes, such as test scores, will be treated as continuous variables and will be evaluated using hierarchical linear models of the general form described in §F.3.2.1.A. Dichotomous categorical outcomes will be evaluated using hierarchical logistic models of the general form described in §F.3.2.1.B.

#### ***F.3.2.2. Secondary Patient Outcomes***

As discussed in §C.2.3, we will evaluate the effect of program participation in Intervention on various postoperative outcomes of patients undergoing surgery in hospitals associated with those programs compared to patients in hospitals associated with programs that did not participate in the Intervention. This evaluation will only be carried out among programs associated with hospitals that participate in the ACS NSQIP program.

Patient outcomes are dichotomous variables indicating whether a patient experienced each of the following postoperative complications:

- 30 day postoperative death or serious morbidity
- 30 day postoperative death
- 30 day postoperative morbidity (NSQIP composite)
- 30-Day Postoperative Surgical Site Infection (SSI)
- 30-Day Postoperative Respiratory Complications (composite of pneumonia, intraoperative or postoperative unplanned intubation, pulmonary embolism, ventilation  $\geq 48$  hours)
- 30-Day Postoperative Pneumonia
- 30-Day Postoperative Urinary Tract Infection
- 30-Day Postoperative Renal Failure
- 30-Day Postoperative Venous Thromboembolism (deep vein thrombosis and/or pulmonary embolism)
- 30-Day Postoperative Stroke
- 30-Day Postoperative Myocardial Infarction
- 30-Day Intra- and Postoperative Transfusion
- 30-Day Postoperative Sepsis/Septic Shock
- 30-Day Postoperative Unplanned Return-to-Operating Room
- 30-Day Postoperative Unplanned Readmission
- Non-Home Discharge
- Failure to Rescue
- 30-Day Postoperative Cardiac Complications

Each outcome will be modeled separately using hierarchical logistic regression models of the general form

$$\log \left( \frac{Pr(\text{complication}_{ijk} = 1 | TREAT_{ijk}, x, z, \zeta_j^{(2)}, \zeta_r^{(3)})}{(1 - (Pr(\text{complication}_{ijk} = 1 | TREAT_{ijk}, x, z, \zeta_j^{(2)}, \zeta_r^{(3)})))} \right) =$$

$$\beta_0 TREAT_j + \beta_1 x_{1ijr} + \beta_2 x_{2ijr} + \cdots + \beta_k x_{kijr} + \gamma_1 z_{1jr} + \cdots + \gamma_m z_{mjr} + \zeta_j^{(2)} + \zeta_r^{(3)}$$

where  $complication_{ij}$  is the outcome of patient  $i$  in hospital  $j$  that is associated with program  $r$ ;  $x_{1ijr} \dots x_{kjr}$  are patient covariates,  $z_{1jr} \dots z_{mjr}$  are hospital-level covariates to be adjusted for,  $z_{1r} \dots z_{wr}$  are program-level covariates including sampling stratification variables,  $\zeta_j^{(2)}$  are hospital-level intercepts and  $\zeta_r^{(3)}$  are program-level covariates. Patient-level covariates for risk-adjustment will be based on outcome-specific risk-adjustment models developed by NSQIP for use in their Semi-Annual Reports (SAR).

#### **F.3.3.1. Pre-Post with Control Analyses**

As an additional perspective, we may explore analyses that take baseline rates of programs in each arm into account. In these analyses, rather than identifying the intervention on the basis of a post-only comparison between Intervention and Control, we examine whether *improvement* in outcomes was greater among programs randomized to Intervention relative to improvement in outcomes among programs randomized to Control. These analyses may be executed by regressing pre-post differences in outcomes on study arm assignment and controls for sampling strata as well as other covariates at the discretion of Investigators and analysts, as appropriate to the data. We do not take this approach as our main analytic strategy because the Intervention under investigation is largely untested. Prospective power calculations would require two assumptions: (a) the rate of secular improvement in the absence of the intervention; and (b) the effectiveness of the intervention or its components to estimate the expected difference in mean rates within the Intervention group.

